9.6 Statistical Methods

Primary Endpoint

The analysis for the primary endpoint AHI will be on the natural log scale. Natural log-transformed fold change from baseline values for AHI will be analyzed using a linear mixed effects model and the following step wise procedure.

The primary hypothesis will be evaluated by first comparing 180mg MK-7264 versus placebo using data from all two periods. The dependent variable is natural log (treatment/baseline), and the independent variables in the model include terms for treatment, sequence, and period. In addition, the between-treatment difference in log-baseline AHIs ($X_{diff_AB} = \ln(\text{baseline of MK-7264}/\text{baseline of Placebo})$) will be used as a covariate in the model, along with a treatment by X_{diff_AB} interaction; the latter term allows for the fact that the correlation between change from baseline and baseline may differ by treatment. An unstructured covariance matrix will be used to allow for unequal treatment variances and to model the correlation between treatment measurements within each subject via the REPEATED statement in SAS PROC MIXED. If the model fails to converge a simpler covariance structure, Type=CS, will be used. Kenward and Roger's method will be used to calculate the denominator degrees of freedom for the fixed effects (DDFM=KR). Least square means and 95% confidence intervals will be calculated for MK-7264 and placebo. These least squares means and 95% CIs will be exponentiated to obtain the geometric mean fold change from baseline for each treatment. The least squares mean treatment difference (MK-7264 - Placebo) and corresponding 90% CI in natural log transformed change from baseline will be calculated from the model. The treatment difference and CI will be

exponentiated to obtain the geometric mean treatment fold difference (MK-7264/placebo) and corresponding CI. If the upper limit of this 90% CI is less than 1.00, then it will be concluded that the administration of 180 mg MK-7264 has statistically significantly lowered the AHI, thus satisfying the primary hypothesis. This CI will be examined for the containment of 0.70 which translates into a 30% reduction in AHI with treatment.

```
PROC MIXED DATA=all;  
  CLASS seq prd trt subjid;  
  MODEL log(value/base) =seq trt prd xdiff_AB xdiff_AB*trt/ ddfm=kr;  
  REPEATED trt/SUBJECT= subjid(seq) TYPE=UN;  
  LSMEANS trt/AT xdiff_AB=0 DIFF CL ALPHA=0.1;  
  RUN;
```

The posterior probability that the true mean percent reduction in AHI after multiple doses of MK-7264 compared to placebo exceeds 10, 20, 30, 40 and 50% will also be obtained, assuming normality and a non-informative prior.

Secondary Endpoints

Safety and tolerability will be evaluated following multiple doses of MK-7264 administered to the participants with OSA by clinical assessment of adverse experiences and other safety measurements (vital signs, ECGs, laboratories). Summary statistics will be provided as appropriate.

Exploratory Endpoints

Population pharmacokinetics approach will be utilized for evaluating MK-7264 plasma PK parameters, C_{max}, AUC₀₋₂₄, CL, and t_{1/2}. The population PK results will be presented in a separate memo.

Mean SaO₂: The analysis for the mean SaO₂ will be on the natural log scale. Natural log-transformed fold change from baseline values for mean SaO₂ will be analyzed using the above described model. Baseline is defined as the mean SaO₂ during total sleep time on day-1 for each period. The mean SaO₂ during REM, NREM and Awake time will be analyzed in a similar fashion.

Proportion of the Night SaO₂ <90%: Summary statistics will be provided for the percentage of participants who experience a SaO₂ level less than 90% during the TST by treatment. Summary statistics will also be provided for the proportion of the night during total sleep time in which SaO₂ is <90% by treatment. The proportion of the night SaO₂<90% during various sleep stages, REM, NREM, and Awake time will also be summarized.

Descriptive summary statistics will be provided for the following exploratory endpoints including arousal index, loop gain at various sleep stages, and proportion of stage N1 NREM to TST. Some of these parameters may also be analyzed in models as previously described to explore the effect of MK-7264 on these parameters.

To assess the day time sleepiness and quality of life improvement, descriptive statistics will be provided for ESS, MSQ, and FOSQ scores. The relationship between the AHI and loop gain at different sleep stages and the relationship of AHI and various scores (ESS, MSQ, and FOSQ) will be explored graphically.

To explore the effect of MK-7264 on diastolic (DBP) and systolic blood pressure (SBP), the difference (BP at Lights on – BP at -1.5 hr) will be computed on the original scale. Summary statistics for this difference in the BP for both diastolic and systolic blood pressure readings will be computed.

Analysis of the sleep data from Emerald device will not be a part of the current analysis plan. A separate statistical plan will be drafted, and the results of the analysis will be presented in a separate memo.

Analysis of blood and urine biomarkers and the evaluation of the relationship of genetic variation and response to the treatment and mechanism of disease will not be a part of current analysis plan. Results of these analysis may be presented in a separate memo.

All data will be examined for departures from the assumptions of the model(s), i.e., heteroscedasticity, outliers, and non-independence and nonnormality of the error terms. Suitable data transformations may be applied. Distribution-free methods may be used if a serious departure from the assumptions of the model(s) is observed.

Individual listings for each of the endpoints by treatment will be provided. Baseline summary statistics will also be provided.

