9 STATISTICAL ANALYSIS PLAN

9.1 Statistical Analysis Plan Summary

The analysis for the primary endpoint will be on the natural log scale of the AHI data. Natural log-transformed fold change from baseline values for AHI will be analyzed using a linear mixed effects model. The dependent variable is natural log (treatment/baseline), and the independent variables in the model include terms for treatment, sequence, and period. In addition, the between-treatment difference in baseline AHIs ($X_{diff_AB} = \ln(\text{baseline of MK-7264}/\text{baseline of Placebo})$) will be used as a covariate in the model, along with a treatment by X_{diff_AB} interaction; the latter term allows for the fact that the correlation between change from baseline and baseline may differ by treatment. An unstructured covariance matrix will be used to allow for unequal treatment variances and to model the correlation between treatment measurements within each subject via the REPEATED statement in SAS PROC MIXED. Least square means and 95% confidence intervals will be calculated for each treatment. These least square means and 95% CIs will be exponentiated to obtain the geometric mean fold change from baseline for each treatment. The least square mean treatment differences (MK-7264 - Placebo) and corresponding 90% CIs in natural log transformed change from baseline will be calculated from the model. The treatment differences and CIs will be exponentiated to obtain the geometric mean treatment fold differences (MK-7264/placebo) and corresponding CIs. If the upper limit of this 90% CI is less than 1.00, then it will be concluded that the administration of MK-7264 has statistically significantly lowered the AHI, thus satisfying the primary hypothesis.

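### Section 9.6 promises 95% confidence intervals for each treatment's geometric mean AHI fold change, but its only LSMEANS statement sets ALPHA=0.1 and so gives 90% intervals.

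*Combined protocol and SAP*

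**What the plan says.** Section 9.6 gives the level for the individual treatments: "Least square means and 95% confidence intervals will be calculated for MK-7264 and placebo". It then gives their use: "These least squares means and 95% CIs will be exponentiated to obtain the geometric mean fold change from baseline for each treatment". For the contrast between treatments it asks for a different level: "corresponding 90% CI in natural log transformed change from baseline will be calculated from the model". The summary in Section 9.1 repeats both, with "Least square means and 95% confidence intervals will be calculated for each treatment" for the means and "corresponding 90% CIs in natural log transformed change from baseline will be calculated from the model" for the difference. The 95% is therefore not a slip in one sentence.

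The PROC MIXED code printed in Section 9.6 contains one statement that requests means, differences and limits: "LSMEANS trt/AT xdiff_AB=0 DIFF CL ALPHA=0.1". It has no second LSMEANS statement and no ESTIMATE statement. Nothing in the text says that the code is meant for the difference alone.

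**The concern.** An ALPHA option on an LSMEANS statement governs every limit that the statement prints. Here it governs both the two treatment means and their difference. This is general SAS behaviour and is not described in the documents. The value 0.1 is right for the difference, because the primary rule uses the upper limit of a 90% interval. It is wrong for the treatment means, where the text wants 0.05.

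The per-treatment intervals describe the primary endpoint in each arm: whether AHI moved from its own baseline under MK-7264, and whether it moved under placebo. If the printed limits were put in a table headed 95%, as the text requires, they would be 90% limits that look more precise than they are, and the reader would have no way to tell.

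**Working it through.** **Inputs.** From Section 9.9: 16 completers, log-scale variance 0.36, correlation 0.75 (0.60 and 0.50 in the sensitivity table), geometric mean ratio 0.70, one-sided alpha 0.05. From Section 6.3.1: 8 participants per sequence. Assumed: complete data, and the same correlation between any two of a participant's four AHI values.

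**Degrees of freedom.** With complete data and the unstructured covariance, the model amounts to a separate regression for each treatment, and one for the within-participant difference, on an intercept, sequence and xdiff_AB. That leaves 16 − 3 = 13 degrees of freedom.

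**Check against the plan's own figure.** I simulated this model with success defined as an upper 90% limit below 1.00.

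| Correlation | Power, simulated | Power, Section 9.9 |
|---|---|---|
| 0.75 | 92% | 92% |
| 0.60 | 78% | 78% |
| 0.50 | 70% | 71% |

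The simulated model matches the sponsor's, and ALPHA=0.1 is the right setting for the difference.

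**Width of the treatment-mean limits.** The half-width is t × SE, and the SE is the same at either level, so the ratio of widths is the ratio of t values.

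- Unstructured covariance, 13 df: 1.771 / 2.160 = 0.820, so the limits are 18% narrower.
- The plan also allows a fallback: "If the model fails to converge a simpler covariance structure, Type=CS, will be used". The degrees of freedom then lie between 13 and 26. At 26 df, 1.706 / 2.056 = 0.830, so the limits are 17% to 18% narrower.

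**Size on the AHI scale.** Given xdiff_AB, the variance of one treatment's log fold change is 1.5 × 0.36 × (1 − correlation). At correlation 0.75 the approximate SE is √(1.5 × 0.36 × 0.25 / 16) = 0.092. The simulated mean half-widths below are slightly larger than t × 0.092 because they also carry the estimation of the xdiff_AB slope.

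| Correlation | Half-width, ALPHA=0.1 | Half-width, ALPHA=0.05 |
|---|---|---|
| 0.75 | 0.166 | 0.202 |
| 0.60 | 0.210 | 0.256 |
| 0.50 | 0.235 | 0.286 |

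For a fold change of 0.70:

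- Correlation 0.75: 0.70 × exp(±0.166) gives 0.59 to 0.83; 0.70 × exp(±0.202) gives 0.57 to 0.86.
- Correlation 0.50: 0.70 × exp(±0.235) gives 0.55 to 0.89; 0.70 × exp(±0.286) gives 0.53 to 0.93.

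**Coverage and reading against 1.00.** Simulated coverage of a treatment mean is about 90% with the code's setting and 95% with the promised one. If placebo truly leaves AHI unchanged, its interval excludes 1.00 in about 10% of trials instead of 5%. For an assumed true MK-7264 fold change of 0.85, a value not taken from the documents, the interval excludes 1.00 in about 49% of trials instead of 35% at correlation 0.75, and in about 31% instead of 20% at 0.50.

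**The case against.** The strongest reply is that the text governs, and the text is clear and consistent. Both levels are stated twice and agree. The printed code is visibly a sketch: it has no exponentiation step, no compound-symmetry fallback and no posterior-probability calculation, all of which Section 9.6 requires. Harm needs two further errors: a programmer must follow the code instead of the text, and the limits must then be labelled 95%. The correct limits can also be rebuilt from the printed estimate, SE and degrees of freedom. Finally, no decision rests on these intervals, so speaking of how often they exclude 1.00 treats them as tests that the plan does not make.

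Most of this stands, and it sets the weight of the point. These are descriptive intervals, and the effect is conditional on the code being followed. It does not remove the mismatch. The code is the only programming specification given for the primary endpoint, the plan does not call it illustrative, and it does not tell anyone to recompute the limits by hand. The other steps missing from the code would be noticed because their output would be absent. This one would not, because limits for the treatment means are printed, only at the wrong level. Readers will also compare each arm's interval with 1.00 whether or not the plan calls that a test.

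**Conclusion.** The concern holds as a minor inconsistency between text and code. Run as written, the code gives 90% intervals where Sections 9.1 and 9.6 both require 95%. Two intervals are affected: the AHI fold change on MK-7264 and on placebo. They would be 17% to 18% too narrow on the log scale if reported as 95%. That ratio depends only on the degrees of freedom; the limits on the AHI scale also rest on the planned variance, the assumed equal correlations and complete data. Point estimates, the 90% interval for the difference, the rule that its upper limit be below 1.00, power and type I error do not change.

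Mean SaO2 during total sleep time "will be analyzed using the above described model", so the same statement could carry over there. No confidence level is promised for SaO2, so that is a matter to clarify and not a second contradiction.

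**What to change.** Replace the single statement with two, both evaluated at xdiff_AB=0:

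- `LSMEANS trt / AT xdiff_AB=0 CL ALPHA=0.05;` from which the treatment means and their limits are reported.
- `LSMEANS trt / AT xdiff_AB=0 DIFF CL ALPHA=0.1;` from which only the difference is reported. This statement will still print 90% limits for the means, and these should not go into the tables.

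If per-treatment 95% intervals are also wanted for mean SaO2, state the level in Section 9.6 and use the same pair of statements. The cost is one added line of code, with no new data and no change to the primary test or the sample size.

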9.7 Interim Analyses

No Interim analyses are planned

9.8 Multiplicity

No multiplicity adjustment procedure will be applied, as there is only one hypothesis to be tested

9.9 Sample Size and Power Calculations

Primary endpoint: AHI

A study with 16 completing subjects in a 2-period crossover design has ~92% probability to detect (alpha=0.05, 1-sided) a statistically significant difference between treatments if the true underlying geometric-mean ratio, GMR (MK7264/Placebo), is 0.70 (which translates into a 30% reduction in AHI after treatment with MK-7264 compared to placebo). This estimate is based on 2000 simulated trials of size N=16 in which individual AHI values were generated assuming a true reduction in AHI of 30%, total variance of 0.36 (natural log scale) and between-measurement correlation of 0.75. These variance estimates were obtained from MK-4305 P036. Fold-change from baseline was then calculated for each trial and analyzed

with the above-described linear mixed effects model. The power was obtained as the percentage of trials showing a statistically significant between-treatment difference.

Power calculations

| Sample size | GMR=0.70 30% reduction Correlation=0.75 | GMR=0.70 30% reduction Correlation=0.60 | GMR=0.70 30% reduction Correlation=0.50 |
|-------------|---|---|---|
| N=16 | 92 | 78 | 71 |

10 SUPPORTING DOCUMENTATION AND OPERATIONAL CONSIDERATIONS

10.1 Appendix 1: Regulatory, Ethical, and Study Oversight Considerations

10.1.1 Code of Conduct for Clinical Trials

Merck Sharp and Dohme Corp., a subsidiary of Merck & Co., Inc. (MSD)

Code of Conduct for Interventional Clinical Trials

I. Introduction

A. Purpose

MSD, through its subsidiaries, conducts clinical trials worldwide to evaluate the safety and effectiveness of our products. As such, we are committed to designing, implementing, conducting, analyzing and reporting these trials in compliance with the highest ethical and scientific standards. Protection of participants in clinical trials is the overriding concern in the design of clinical trials. In all cases, MSD clinical trials will be conducted in compliance with local and/or national regulations (eg, International Council for Harmonisation Good Clinical Practice [ICH-GCP]) and in accordance with the ethical principles that have their origin in the Declaration of Helsinki.

B. Scope

Highest ethical and scientific standards shall be endorsed for all clinical interventional investigations sponsored by MSD irrespective of the party (parties) employed for their execution (eg, contract research organizations, collaborative research efforts). This Code is not intended to apply to trials that are observational in nature, or which are retrospective. Further, this Code does not apply to investigator-initiated trials, which are not under the full control of MSD.

II. Scientific Issues

A. Trial Conduct

1. Trial Design

Except for pilot or estimation trials, clinical trial protocols will be hypothesis-driven to assess safety, efficacy, and/or pharmacokinetic or pharmacodynamic indices of MSD or comparator products. Alternatively, MSD may conduct outcomes research trials, trials to assess or validate various endpoint measures, or trials to determine patient preferences, etc.

The design (ie, participant population, duration, statistical power) must be adequate to address the specific purpose of the trial. Participants must meet protocol entry criteria to be enrolled in the trial.

2. Site Selection

MSD selects investigative sites based on medical expertise, access to appropriate participants, adequacy of facilities and staff, previous performance in clinical trials, as well as budgetary considerations. Prior to trial initiation, sites are evaluated by MSD personnel to assess the ability to successfully conduct the trial.

3. Site Monitoring/Scientific Integrity

Investigative trial sites are monitored to assess compliance with the trial protocol and general principles of Good Clinical Practice (GCP). MSD reviews clinical data for accuracy, completeness, and consistency. Data are verified versus source documentation according to standard operating procedures. Per MSD policies and procedures, if fraud, scientific/research misconduct, or serious GCP-noncompliance is suspected, the issues are investigated. When necessary, the clinical site will be closed, the responsible regulatory authorities and ethics review committees notified.

B. Publication and Authorship

Regardless of trial outcome, MSD commits to publish primary and secondary results of its registered trials of marketed products in which treatment is assigned, according to the prespecified plans for data analysis. To the extent scientifically appropriate, MSD seeks to publish the results of other analyses it conducts that are important to patients, physicians, and payers. Some early phase or pilot trials are intended to be hypothesis-generating rather than hypothesis testing, in such cases, publication of results may not be appropriate since the trial may be underpowered and the analyses complicated by statistical issues such as multiplicity.

MSD's policy on authorship is consistent with the recommendations published by the International Committee of Medical Journal Editors (ICMJE). In summary, authorship should reflect significant contribution to the design and conduct of the trial, performance or interpretation of the analysis, and/or writing of the manuscript. All named authors must be able to defend the trial results and conclusions. MSD funding of a trial will be acknowledged in publications.

III. Participant Protection

A. Ethics Committee Review (Institutional Review Board IRB/Independent Ethics Committee IEC)

All clinical trials will be reviewed and approved by an IRB/IEC before being initiated at each site. Significant changes or revisions to the protocol will be approved by the ethics committee prior to implementation, except changes required urgently to protect participant safety that may be enacted in anticipation of ethics committee approval. For each site, the ethics committee and MSD will approve the participant informed consent form.

B. Safety

The guiding principle in decision-making in clinical trials is that participant welfare is of primary importance. Potential participants will be informed of the risks and benefits of, as well as alternatives to, trial participation. At a minimum, trial designs will take into account the local standard of care.

All participation in MSD clinical trials is voluntary. Participants enter the trial only after informed consent is obtained. Participants may withdraw from an MSD trial at any time, without any influence on their access to, or receipt of, medical care that may otherwise be available to them.

C. Confidentiality

MSD is committed to safeguarding participant confidentiality, to the greatest extent possible. Unless required by law, only the investigator, Sponsor (or representative), ethics committee, and/or regulatory authorities will have access to confidential medical records that might identify the participant by name.

D. Genomic Research

Genomic research will only be conducted in accordance with a protocol and informed consent authorized by an ethics committee.

IV. Financial Considerations

A. Payments to Investigators

Clinical trials are time- and labor-intensive. It is MSD's policy to compensate investigators (or the sponsoring institution) in a fair manner for the work performed in support of MSD trials. MSD does not pay incentives to enroll participants in its trials. However, when enrollment is particularly challenging, additional payments may be made to compensate for the time spent in extra recruiting efforts.

MSD does not pay for participant referrals. However, MSD may compensate referring physicians for time spent on chart review to identify potentially eligible participants.

B. Clinical Research Funding

Informed consent forms will disclose that the trial is sponsored by MSD and that the investigator or sponsoring institution is being paid or provided a grant for performing the trial. However, the local ethics committee may wish to alter the wording of the disclosure statement to be consistent with financial practices at that institution. As noted above, all publications resulting from MSD trials will indicate MSD as a source of funding.

C. Funding for Travel and Other Requests

Funding of travel by investigators and support staff (eg, to scientific meetings, investigator meetings, etc.) will be consistent with local guidelines and practices.

V. Investigator Commitment

Investigators will be expected to review MSD's Code of Conduct as an appendix to the trial protocol, and in signing the protocol, agree to support these ethical and scientific standards.

